variants, and copy number variations (CNVs), including both copy number gains and losses, across ~500 genes. The panel will include, but will not be limited to, genes involved in DNA repair systems (e.g. *BRCA1*, *BRCA2*, *PALB2*, *CHEK2*, *ATM*), PIK3CA pathway (e.g. *PIK3CA*, *AKT1*, *PTEN*), estrogen receptor (e.g. *ESR1*). It also allows the quantitative evaluation of tumor mutational burden (TMB) and the analysis of the microsatellite instability (MSI) status.⁹⁷

Transcriptomic analyses

After cellular RNA extraction, RNA quality check and preparation of libraries, RNA will be sequenced with NovaSeq 6000 System. Counts will be analyzed to dissect differential gene expression both at single gene level – through differential gene expression analysis (i.e, Deseq2 method) – and at pathway level – through Gene Set Enrichment Analysis (GSEA), Over Representation Analyses (ORA) and Gene Set Variation Analysis (GSVA).(30,31) The pathway-level analysis will be carried out using the Bioconductor packages fgsea, gsva, and clusterprofiler, taking advantage of HALLMARK, KEGG, and REACTOME gene sets available from GSEA Molecular Signatures Database (http://www.gsea-msigdb.org/gsea/msigdb/collections. jsp). Intrinsic subtypes will be assessed through Absolute Intrinsic Molecular Subtyping (AIMS) algorithm. ^{98–100}

Study duration

Patient enrollment and data collection will start upon approval of the study protocol by the competent ethics committee. All consecutive HR+/HER2- aBC patients treated with first-line ET plus CDK 4/6 inhibitors as per clinical practice in the time interval between January 2016 and December 2030 will be enrolled. The collection and the update of clinical data, medical images and biological samples will continue for an expected duration of 10 years from the enrollment of the last patient. The clinical data, medical images and data obtained from the biological samples will be retained for further 10 years after the end of the study, while the biological samples will be returned to the pathology departments of the Center of origin at the end of the analyses foreseen in the protocol.

Ethical considerations

This study will be conducted according to the Declaration of Helsinki and in compliance with ethical principles regarding human research.

Based on its observational nature, and in accordance with the Italian Ministerial Decree of 30th November 2021, the present study was approved by the Ethics Committee of the Sponsor Institution (Fondazione IRCCS Istituto Nazionale dei Tumori), and it was subsequently adopted by all the participating centers. Based on

Article 110bis of the Italian Privacy Code (Legislative Decree of 30 June 2003, n.196 updated 01 May 2024), the privacy impact assessment of the study is performed at the level of the Sponsor center and published on Institutional website, therefore no additional assessment by the other centers participating in the study is required.

References

- 2. AIRTUM. I numeri del cancro in Italia 2023.

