Digitalized pathology slide: hematoxylin and eosin (HE) slides coming from diagnostic biopsy or surgical specimens will be digitalized and collected in a pre-defined folder. Both slides from primary tumor and from metastatic sites that underwent biopsy assessment will be collected, if available. If more than one metastatic biopsy has been performed during the course of patient's disease, all the HE slides should be collected, if available. If a patient did not undergo neoadjuvant treatment, diagnostic biopsy of the breast or surgical tumor slide could be collected equivalently; otherwise, the diagnostic biopsy performed before treatment initiation should be taken.

(4) Translational sub-study

Objectives and endpoints of the sub-study

Primary objective:

- To find the mutational status of a gene, or a subset of genes, associated with differential survival outcomes (rwPFS, TTNT-D, TTC-D and OS) of HR+/HER2- aBC patients treated with first-line ET+CDK4/6i;
- To find transcriptomic differential gene expression, or differential expressed pathways, associated with differential survival outcomes (rwPFS, TTNT-D, TTC-D and OS) of HR+/HER2- aBC treated with first-line ET+CDK4/6i.

Secondary objectives:

- To test the effect of PAM50 intrinsic subtype on survival outcomes (rwPFS, TTNT-D, TTC-D and OS) of HR+/HER2- aBC patients treated with first-line ET+CDK4/6i;
- To combine genomics and transcriptomics features with clinical data and radiomics and pathomics features, to build a model able to predict prognosis of HR+/HER2- aBC patients treated with first-line ET+CDK4/6i;
- To test the association between agnostic features included in radiomics model and transcriptomic pathways and mutational status.

Study Population

The same inclusion and exclusion criteria adopted for the RWD sub-study will be adopted for the present sub-study, for the only exception of the following inclusion criterion:

Availability of adequate tumor sample (see Data Collection below) from biopsy of metastatic sites and/or from primary tumor biopsy and/or from surgery specimen.

Data collection

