For the "Translational sub-study" purposes, tumor samples related to patients enrolled in the RWD sub-study will be considered. If multiple tumor samples are available, the ones to be used for the study has to be chosen as specified in the section "Translational sub-study". Tumor materials have to be shipped to the Sponsor center at the moment of the conduction of translational analyses, attributing the same pseudonymized code used for the other sub-study. The remaining unused tumor tissue will be sent back to the pathology laboratory at the end of the study.

Statistical considerations

Statistical design

Based on pivotal trials showing a statistically significant OS advantage for ribociclib and abemaciclib, but not for palbociclib in the endocrine resistant setting, and clinically meaningful OS advantage for ribociclib and abemaciclib, but not for palbociclib in the endocrine sensitive setting, we will hypothesize a difference of 20% in terms of OS between ribociclib versus palbociclib and between abemaciclib and palbociclib. To detect this difference with 80% power with a two-sided alpha error of 0.05, a sample size of 3258 patients reaching 977 OS events will be required. The prognostic role of CDK4/6i drug will be weighed for clinically and biologically relevant characteristics.⁸⁹

Since the number of patients enrolled in the other sub-studies depends on the sample size of the RWD sub-study, no formal statistical calculation has been performed for 2 to 5 PALMARES-2 sub-studies.

Statistical methods

Version 1.1, 01Aug2024

Standard descriptive statistics will be used to describe clinical and biological patients' characteristics. The median and interquartile range (IQR) were reported for continuous variables. Categorical variables were summarized as percentages of available data. To evaluate differences, in terms of clinic-pathological characteristics, among different CDK4/6i groups, we will use the Kruskal-Wallis Rank Sum test for

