continuous variables and the Chi-square and Fisher exact tests for categorical variables. Unpaired t-test will be used to compare numeric variables, at baseline and different timepoints. Classic survival analysis methods will be used to evaluate patient survival outcomes and survival curves will be obtained through the Kaplan–Meier method. Follow-up times will be estimated using the reverse Kaplan–Meier method. Multivariable analysis will be performed through Cox regression modeling to estimate the effects of covariates. To homogenize patients' characteristics among treatment groups, additional adjustment techniques will be eventually used, such as propensity score matching (PSM) and inverse probability of treatment weighting (IPTW). Estimated weights will be then incorporated into a weighted Cox regression model to estimate rwPFS. Area Under the ROC Curve (AUC) values of the models will be calculated using the Caret and pROC R package and compared using Delong's test.

Patients with missing outcome data will be excluded from the analysis. Covariates whose values will be missing in less than 20% were imputed by using the median or the mode value (for numerical or categorical variables, respectively), while covariates with missing values exceeding 20% will be excluded from the present analysis. 90 All statistical tests will two-tailed, and a p value (P) <0.05 was considered as significant. Statistical analyses will be performed using R software and R Studio (version 4.1.2).

Image omics and model generation methodology

Radiomics Methodology

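### The protocol's blanket p<0.05 rule also governs sub-study 4's primary search of about 500 genes, expression and pathways against four survival endpoints, with no false-discovery control

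*Protocol*

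**What the plan says.** Section (4), Translational sub-study, lists two primary objectives. The genomic one is "To find the mutational status of a gene, or a subset of genes, associated with differential survival outcomes (rwPFS, TTNT-D, TTC-D and OS"), and the transcriptomic one is "To find transcriptomic differential gene expression, or differential expressed pathways, associated with differential survival outcomes (rwPFS, TTNT-D, TTC-D and OS"). Neither names a gene, a gene set or a leading endpoint.

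Biological analyses methodology sets the breadth. Under Genomic analyses the panel reports several kinds of variant, "including both copy number gains and losses, across ~500 genes". Under Transcriptomic analyses the plan is that "Counts will be analyzed to dissect differential gene expression both at single gene level"; the tool named for this step is DESeq2. Pathways are examined with three enrichment methods, "taking advantage of HALLMARK, KEGG, and REACTOME gene sets".

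The decision rule is in Statistical considerations, Statistical methods: "All statistical tests will two-tailed, and a p value (P) <0.05 was considered as significant". It makes no exception for any sub-study. Statistical design adds that "no formal statistical calculation has been performed for 2 to 5 PALMARES-2 sub-studies". The protocol nowhere mentions a multiplicity adjustment, an adjusted p-value, a false discovery rate, or a validation set for the gene findings. The 80:20 training and test split belongs to the imaging and multimodal models.

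**The concern.** A threshold of 0.05 per test limits the error of one pre-specified comparison. It does not limit the error of a search, where the result is whichever items cross the line. Here the list of genes is the primary result of the sub-study, so the threshold alone determines how much of that list can be trusted.

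This is also more than a detail left for a statistical analysis plan. The protocol is not silent: it fixes the unadjusted rule for all tests. An analysis plan that used false-discovery control would depart from the protocol, and one that followed the protocol would declare genes at 0.05. At stake is a primary finding whose expected number of false entries grows with the number of genes and endpoints tested.

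**Working it through.** The protocol gives no sample size, power or error rate for sub-study 4, so it has no figure of its own to reproduce.

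**Inputs from the protocol:** about 500 genes (Genomic analyses); four endpoints (section 4); two-sided 0.05 per test (Statistical methods).

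**Inputs assumed:** the number of truly prognostic genes, the power per true gene, the number of testable genes and the number of expressed genes. None of these is in the protocol, so ranges are shown.

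**1. Expected false declarations if no gene is prognostic** (number of tests × 0.05)
- One endpoint, 500 genes: 500 × 0.05 = 25.
- Four endpoints: 4 × 25 = 100 gene-endpoint pairs. Correlation between endpoints does not change this expectation.
- Distinct genes false on at least one endpoint: 25 if the endpoints are perfectly correlated, up to 500 × (1 − 0.95⁴) = 500 × 0.185 = 93 if they are independent. Simulation gives 47 at a correlation of 0.9 and 65 at 0.7.
- If only 50 to 100 genes are altered often enough to test: 2.5 to 5 per endpoint, 10 to 20 pairs over four endpoints.

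**2. Share of declared genes that are false, one endpoint**

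With m genes tested, m₁ truly prognostic and power π, the false share is (m − m₁) × 0.05 / [(m − m₁) × 0.05 + m₁ × π].

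| m | m₁ | π | Expected false / true | False share |
|---|---|---|---|---|
| 500 | 20 | 80% | 24 / 16 | 60% |
| 500 | 20 | 30% | 24 / 6 | 80% |
| 500 | 50 | 80% | 22.5 / 40 | 36% |
| 500 | 50 | 30% | 22.5 / 15 | 60% |
| 500 | 100 | 80% | 20 / 80 | 20% |
| 100 | 10 | 80% | 4.5 / 8 | 36% |
| 50 | 10 | 80% | 2 / 8 | 20% |

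For 500 genes the share is one half at m₁ = 500 × 0.05 / (π + 0.05): 25/0.85 = 29 genes at 80% power, 25/0.55 = 45 at 50%, and 25/0.35 = 71 at 30%. With fewer true genes than that, most declared genes are false.

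**3. A hit on any of the four endpoints**

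Simulation with 500 genes, 80% power per endpoint and endpoint correlation from 0 to 0.9 gives a false share of 83–90% with 10 true genes, 72–81% with 20, and 49–62% with 50.

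**4. Is low power plausible?**

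The background section puts Rb loss at 3–9% and several receptor tyrosine kinase alterations below 10%. By Schoenfeld's formula, power = Φ(√[d·p(1 − p)] × |ln HR| − 1.96). For p = 3% and an assumed hazard ratio of 1.5:
- d = 977 (the OS event target of the whole real-world sub-study): √28.4 × 0.405 − 1.96 = 0.20, power 58%.
- d = 300 (assumed, for a subset with tissue): √8.73 × 0.405 − 1.96 = −0.76, power 22%.

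**5. Transcriptome**

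For an assumed 15,000 to 20,000 genes, all null, a raw threshold gives 750 to 1000 false genes per contrast.

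**6. Effect of the remedy**

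In the simulation of step 3, Benjamini-Hochberg at 5% over the 2000 gene-endpoint pairs lowers the false share among flagged genes to about 7–9% with 10 to 50 true genes. It is slightly above 5% because the procedure controls pairs while the count is of genes. With 20 true genes it retains about 7 to 14.

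**The case against.** **The analysis plan may settle it.** Only the protocol is at hand, and the choice of procedure, families, frequency floor and endpoint order is often made in an analysis plan. That stands for those details: their absence alone is not an error. It does not stand for the p<0.05 sentence, which the protocol states without exception.

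**The sentence was meant for the classical tests.** It closes a section on rank, chi-square, t and Cox methods, and the omics work has its own section. That is a fair reading of intent, but the omics section supplies no other rule, and a search for genes associated with survival would itself use survival models. For expression the objection carries more weight: the protocol names the DESeq2 workflow but does not say whether raw or adjusted p-values are thresholded. The 750 to 1000 figure holds only for raw p-values and an assumed gene count, so it should not be read as a prediction.

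**A reader might infer that the gene list must be mostly chance.** The documents do not support that as a general statement. Counting under a complete null makes every hit false by construction, and the number of truly prognostic genes is unknown. With 50 true genes among 500, or 10 among 50 to 100 testable ones, the false share at 80% power on one endpoint is 20–36%.

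**A reader might infer that falsely declared genes then enter the models of sub-studies 3 to 5.** No section says so. Those sub-studies use genomic data, not a list filtered at p<0.05; the multimodal models are trained and tested with cross-validation and a held-out fifth of the cohort; and in some imaging objectives mutation status is the outcome to be predicted.

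**Conclusion.** The point holds for the decision rule. As written, the protocol applies an unadjusted 0.05 to a primary objective that is an open search over about 500 genes, plus expression and pathways, against four unranked endpoints. The firm result is 25 false genes per endpoint and 100 false gene-endpoint pairs if all 500 genes are tested and none matters, or 2.5 to 5 per endpoint if only 50 to 100 are testable.

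That false genes form the majority is conditional. It follows when few genes are truly prognostic, fewer than about 29 of 500 at 80% power or 71 at 30% on one endpoint, and it need not follow otherwise. The transcriptome figure is conditional on raw p-values. No effect on the prediction models of the other sub-studies is claimed.

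**What to change.** Amend the significance sentence in Statistical methods, where the rule sits, so that p<0.05 does not govern the sub-study 4 searches, and cross-refer to it from Genomic analyses and Transcriptomic analyses. A change in the omics section alone would leave the two sections in conflict. Then state:

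- that a gene or pathway is declared only by a false-discovery-rate procedure, for example Benjamini-Hochberg at 5%, on adjusted p-values;
- the families to which it applies: mutations, expression and pathways, each separately;
- how the four endpoints enter: either one lead endpoint, with effect sizes on the other three as support, or all four endpoints inside the family.

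The lead endpoint is for the sponsor to choose; the protocol gives no event counts for rwPFS, TTNT-D or TTC-D on which to base a recommendation. A minimum alteration frequency is optional and also the sponsor's choice. It would cut the number of tests, but the protocol's own range for Rb loss starts at 3%, so a floor could remove a leading candidate.

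The cost is protocol wording, with no new patients or data. The price in results is that fewer genes will be declared, including some true ones.

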Finally, also the use of immunotherapy could represent a potential option for pre-treated HR+/HER2- aBC. The phase 2 PACE trial demonstrated potential activity of the immune-checkpoint inhibitor avelumab plus fulvestrant compared with fulvestrant alone or the combination of fulvestrant and palbociclib, in patients with HR+/HER2- aBC progressing after first-line ET+CDK4/6i, with a statistically significant advantage in terms of PFS (8.1 months for triplet vs 4.6 for doublet vs 4.8 for Fulvestrant alone), opening an opportunity for immunotherapy in selected patients in this setting.⁸¹

Together, these data indicate that several therapeutic options are available, or may become available soon, for the treatment of HR+/HER2-aBC patients in different lines of therapy. However, few reliable predictive biomarkers actually exist for optimizing the treatment trajectory of individual patients and finally improving overall survival (OS). Since there is no accepted evidence on which is the best choice after CDK4/6i+ET for HR+/HER2-aBC patients, clinicians are left alone during the treatment decision, causing fragmentation in therapeutic practice between cancer centers and even among individual oncologists.

The importance of real world data (RWD) in HR+/HER2- aBC patients treated with ET+CDK4/6i

Recently, there has been a growing interest in observational real-world studies, due to their ability to observe the effects of a given treatment even outside the ideal clinical conditions that characterize RCTs. These types of studies also allow sub-analyses to be carried out in certain subgroups, usually underreported in RCTs, and Version 1.1, 01Aug2024

Pag. 10 di 32

to study biomarkers potentially useful for establishing treatment efficacy. This is particularly relevant in the context of established clinical settings, such as HR+/HER2- aBC patients who are candidates for first-line therapy, where it is difficult, in terms of ethics and pharmaco-economics, to conduct comparison prospective randomized trials to address specific clinical questions.

In this context, and in view of the long average duration of patients' exposure to this class of drugs, it is of primary importance to more accurately establish the real-world efficacy and toxicity of the three CDK4/6i.

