PALMARES-2 is a retrospective/prospective, observational, multicenter, population-based study, aiming at providing real-world evidences on HR+/HER2- aBC patients treated with first-line CDK4/6i plus ET.

The present study has the objective to collect data coming from different sources, i.e. RWD, medical images and biological samples, from patients treated with CDK4/6i as first-line of therapy for HR+/HER2- aBC. In consideration of the complexity of data collected and different objectives of the study, this master protocol foresees different sub-studies, which encompasses different methodologies for data collection, data extraction and analyses. The sub-studies will be described in the following sections.

[figure not shown]

Figure 1. PALMARES-2 graphical abstract. CBC: cell blood count; CT: computed tomography; ET+CDK4/6i: endocrine therapy plus cyclin-dependent kinase 4/6 inhibitor; FdG-PET: fluorodeoxyglucose positron emission tomography; FFPE: formalin-fixed paraffin-embedded; HE: hematoxylin-eosin; HR+/HER2- aBC: hormone receptor-positive, human epidermal growth factor receptor 2-negative advanced breast cancer; PD: progressive disease; RWD: real-world data.

(1) Real world data (RWD) PALMARES-2 sub-study

Objectives and endpoints of the sub-study:

Primary objectives:

- To test the difference in terms of OS between the group of patients receiving ribociclib and palbociclib;
- To test the difference in terms of OS between the group of patients receiving abemaciclib and palbociclib.

Secondary objectives:

- To test the difference in terms of OS between the group of patients receiving abemaciclib and ribociclib.
- To determine the real-world progression-free survival (rwPFS), time to next treatment or death (TTNT-D), time to chemotherapy or death (TTC-D) and OS in the real-world setting;
- To test the difference in terms of rwPFS between the group of patients receiving ribociclib and palbociclib;
- To test the difference in terms of rwPFS between the group of patients receiving abemaciclib and palbociclib;
- To test the difference in terms of rwPFS between the group of patients receiving abemaciclib and ribociclib;
- To test the difference in terms of TTNT-D between the group of patients receiving ribociclib and palbociclib;
- To test the difference in terms of TTNT-D between the group of patients receiving abemaciclib and palbociclib;
- To test the difference in terms of TTNT-D between the group of patients receiving abemaciclib and ribociclib;

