This sub-study encompasses the collection of tumor samples of patients enrolled in the PALMARES-2 RWD sub-study. At least one formalin-fixed paraffin-embedded tumor block will be collected from diagnostic biopsy or surgical specimens, performed for diagnostic purposes as per clinical practice. Both tumor samples from primary tumor and from metastatic sites underwent biopsy will be collected, if available. If more than one metastatic biopsy has been performed during the course of patient's disease, all the non-stained slides and/or tumor blocks should be collected, if available. If a patient did not undergo neoadjuvant treatment, diagnostic biopsy of the breast or surgical tumor slide could be collected equivalently; otherwise, the diagnostic biopsy performed before treatment initiation should be taken.

(5) Second and further lines sub-study

Objectives and endpoints of the sub-study

Primary objective:

To build a model based on clinical, radiomics and pathomics data to select the best treatment option in terms of OS in HR+/HER2- aBC patients progressing after first-line ET+CDK4/6i.

Secondary objectives:

- To build a model based on clinical data to select the best treatment option in terms of OS in HR+/HER2- aBC patients progressing after first-line ET+CDK4/6i.
- To build a model based on clinical, radiomics, pathomics, genomics and transcriptomics data to select the best treatment option in terms of OS in HR+/HER2- aBC patients progressing after firstline ET+CDK4/6i.
- To assess the efficacy in terms of rwPFS and OS of second and subsequent line of therapy in a realworld setting of HR+/HER2- aBC patients progressing after first-line ET+CDK4/6i.

Study Population

The same inclusion and exclusion criteria adopted for the RWD sub-study will be applied for the present sub-study, for the only exception of the following inclusion criteria: Version 1.1, 01Aug2024

- Clinical, biochemical or radiological progression on CDK4/6i+ET first-line treatment
- Second-line therapy start after CDK4/6i+ET progression
- Data availability about at least one of the subsequent lines, including at least the treatment line of therapy, treatment start date, treatment progression date or last follow up, type of treatment and drug used.

Data collection

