The study involves the collection of RWD of patients enrolled in the PALMARES-2 RWD study, who started a second line therapy after CDK4/6i progression. Data will be collected at the study centers in the same manner of RWD sub-study. Data collected within this sub-study will include the type of treatment performed (i.e. ET-based therapy, chemotherapy, other) and line of therapy for metastatic disease for which the treatment has been performed; treatment start date and progression date. Data derived from medical images and biological samples collected in the context of sub-study (3) and (4) will be used to pursue the objectives of this sub-study.

Study procedures

Informed consent process and patients' enrollment

Patients who are alive at the time of study conduction will be asked to sign the informed consent for the study partecipation and for treatment of personal data for research purposes, during the first clinical visit. Patients with available material to conduct analyses for the translational sub-study will be asked to the use of data generated from available material for the scientific purposes planned for the present study. It will also be asked to consent to receive unexpected genetic-hereditary information, should it emerge from the analysis of tumor samples.

For patients who are not alive at the moment of study initiation and data collection, the study will adhere to the UE-Reg 2016/679 - GDPR rules for the protection of personal data. In accordance with the Declaration of Helsinki and other applicable regulations, a subject, or his/her legal representative, has the right to withdraw from the study at any time and for any reason without prejudice to his/her future medical care. 88

Data protection procedures

Patients are assigned by the local investigator a unique progressive identifier code, that will be used for all the tasks implied in the study. The pseudonymization procedure will ensure the unique identification of patients still keeping adequate data security. This pseudonymized code will used to save medical images

once shared with the Sponsor center. The same code used to mark biological samples at the moment of the shipment to the centralization for analyses conduction.

Clinical data collection and management

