We will use several architectures, including logistic regression, classification and regression trees, random forest, multi-layer perceptron, gradient boosted trees (XGBoost), gradient boosting machines (LightGBM) and attentive tabular networks TabNet and we will compare their performance to heuristically decide on the best model choice for follow-up experiments. Our modelling experiments will include different combinations of input embeddings, with concatenation of each data stream permutation to produce fusion embeddings and train models using single-modality or multi-modality of input combinations. All models will be trained multiple times with multiple different data splits to repeat the experiments and compute average metrics and SDs. All defined models will be trained and tested to evaluate the advantage of multimodal predictive systems, as compared to single modality ones for the pre-established classification prediction. To assess model performance, different metrics will be used, including AUC, Sensitivity and Specificity, which will be calculated on the training set through 10-fold cross-validation and on the test set, which will be obtained by randomly splitting the entire cohort in a 80:20 way. The hyperparameter combinations of individual models, such as maximum depth of the trees, number of estimators and learning rate, will be selected within each training loop using a fivefold cross-validated grid search on the training set.^{94,95}

Since these complex models are considered as "black boxes", since they make decisions without clear reasoning, explainability techniques will be adopted to provide insights into how models make predictions, guaranteeing human interpretability. In particular, SHapley Additive exPlanations (SHAP) techniques will be used for both global and local explanations. ⁹⁶

Biological analyses methodology

Genomic analyses

A next generation sequencing (NGS) panel (Oncomine Comprehensive Assay Plus) will be used to perform analysis of various single-gene variants, such as single nucleotide variations (SNVs), indels, fusions, splice Version 1.1, 01Aug2024

Pag. 26 di 32

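### Sub-study 5 sets out to select the best post-progression treatment for OS, but the only multimodal modelling method stated is outcome classification assessed by discrimination metrics

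*Protocol*

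**What the plan says.** The primary objective of sub-study 5 is "To build a model based on clinical, radiomics and pathomics data to select the best treatment option in terms of OS" among patients progressing after first-line ET+CDK4/6i. Two secondary objectives repeat the aim, one with clinical data alone and one adding genomics and transcriptomics.

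Under Master protocol study design: "PALMARES-2 is a retrospective/prospective, observational, multicenter, population-based study". The background on therapy after progression says that the lack of accepted evidence leaves the choice to clinicians, "causing fragmentation in therapeutic practice between cancer centers and even among individual oncologists".

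The method for combining data types is under Multimodal integration, which builds on Radiomics Methodology and Pathomics Methodology. It lists classifiers such as logistic regression, random forest and gradient boosting, and states: "To assess model performance, different metrics will be used, including AUC, Sensitivity and Specificity". The stated purpose is to "evaluate the advantage of multimodal predictive systems, as compared to single modality ones for the pre-established classification prediction".

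Adjustment for differences between treatment groups appears in the general Statistical methods, which plan multivariable Cox regression and add that "additional adjustment techniques will be eventually used, such as propensity score matching (PSM) and inverse probability of treatment weighting (IPTW". The estimated weights then enter a Cox model for rwPFS.

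Under Data collection for sub-study 5: "Data collected within this sub-study will include the type of treatment performed (i.e. ET-based therapy, chemotherapy, other", followed by line of therapy and the start and progression dates. The eligibility text also requires the drug used. The Medical imaging sub-study collects CT or PET at the start of each later line for this purpose.

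**The concern.** To select a treatment, one must compare what a patient's OS would be under each of the available options. To predict an outcome, one need only say who will do well under the treatments actually given. The protocol's own wording keeps the two apart: the imaging and translational sub-studies aim to predict prognosis, whereas sub-study 5 aims to select.

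If second-line choice follows prognosis, treatment carries information about how ill the patient was. A model can use that information to discriminate well and still order the treatments wrongly. The protocol recognises this problem elsewhere: in comparing the three CDK4/6 inhibitors, it faults an earlier national registry comparison for possibly leaving confounding by drug choice uncorrected.

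At stake is whether a model reported as choosing treatment for OS has been assessed on that task.

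**Working it through.** The protocol states no figure for sub-study 5, and says that no formal sample size calculation was made for sub-studies 2 to 5. There is therefore no number to reproduce. The check sets the sections side by side and then illustrates the principle.

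**1. Objective against method**

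| Element | What sub-study 5 needs | What the protocol states |
|---|---|---|
| Question | OS under alternative treatments | Classification of an outcome (Multimodal integration) |
| Role of treatment | The contrast of interest | Not named as an input or a contrast in the modelling sections |
| Feature selection | Keep variables that drive treatment choice | Screening against two outcome groups, then LASSO and/or MRMR (Radiomics Methodology) |
| Confounding control | Linked to OS and to the selection model | Optional PSM/IPTW; weights assigned to rwPFS (Statistical methods) |
| Assessment | OS under the recommended versus other treatment | AUC, sensitivity and specificity, in an open list |

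**2. Can AUC reveal a wrong treatment ranking?** A simulation with n = 400,000, all inputs assumed. X is a measured and U an unmeasured prognostic factor, both standard normal.

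- Log-odds of receiving option A: 0.5X + gU
- Log-odds of death: X + U − 0.3A, so A truly helps (odds ratio given X and U: exp(−0.3) = 0.74)
- Fitted model: logistic regression of death on X and A

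| g | AUC | Fitted OR for A | OR if A were randomised | Option favoured |
|---|---|---|---|---|
| 0 | 0.704 | 0.77 | 0.77 | A (correct) |
| 0.5 | 0.704 | 1.15 | 0.79 | not A |
| 1.0 | 0.713 | 1.57 | 0.77 | not A |
| 1.5 | 0.724 | 1.93 | 0.78 | not A |

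Between the first two rows AUC is unchanged while the recommendation reverses. As g rises further, AUC improves and the odds ratio moves further from the truth. Discrimination therefore does not reveal the error. In the first row choice depends only on the measured X, and the outcome model recovers the right answer.

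**3. How far could a crude comparison be off?** For two equally effective treatments and a prognostic factor left out altogether, with death hazard ratio HR and prevalence p1 and p0 in the two groups, the apparent HR at the start of follow-up is approximately (p1·HR + 1 − p1) / (p0·HR + 1 − p0).

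- Assumed HR 2.0, 60% versus 20%: (1.2 + 0.4)/(0.4 + 0.8) = 1.6/1.2 = 1.33
- Assumed HR 1.5, 40% versus 30%: (0.6 + 0.6)/(0.45 + 0.7) = 1.2/1.15 = 1.04

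The range runs from material to negligible. It describes an unadjusted contrast, not the planned models, and so does not size the bias in sub-study 5.

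**The case against.** The case for the plan has real weight.

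- **The modelling sections do not name sub-study 5.** The phrase "as compared to single modality ones for the pre-established classification prediction" fits the imaging sub-study most directly, which plans explicit classifiers. The metric list is also open. A reader might infer that the protocol fixes AUC as the sole test of the treatment-selection model; it does not. What stands is that no other method is given for the combined clinical, radiomics and pathomics model, and no metric named measures a treatment rule.
- **Outcome models can adjust.** A reader might infer that the listed learners can never separate treatment effect from confounding. That is too strong. A model containing treatment and the measured confounders, compared across treatment values, is a recognised adjustment, as the first simulation row shows. AUC still cannot tell whether the adjustment is enough.
- **Confounding is not ignored.** PSM and IPTW sit under a study-wide heading, and nothing excludes their use here. Nothing links them to OS or to the selection model either.
- **Relevant data are collected.** Drug used, second-line start date and imaging at each line are covered, and the RWD sub-study plans blood parameters at progression. Performance status at second-line start is not listed.
- **The simulation uses an unmeasured factor.** Weighting would fail under the same factor, so the simulation shows a limit of AUC and not the superiority of IPTW.
- **Detail belongs in an SAP.** The confounder set, the learner and the overlap rule can be left there. The mismatch between the stated objective and the stated assessment is in the protocol itself.

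**Conclusion.** The point holds as a mismatch between objective and stated method. Sub-study 5 asks a comparative OS question in a non-randomised cohort; the method given for the data it combines is outcome classification, the named metrics measure discrimination, and the one use specified for propensity weights is rwPFS. Followed as written, the assessment could not show whether the recommended treatment is the better one.

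This rests on two readings: that Multimodal integration is the method intended for sub-study 5, since no other is given, and that treatment after progression is chosen at least partly by prognosis.

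The size of the bias is unknown. A reader might infer that the model will favour whatever fitter patients received, or that the apparent HR of 1.33 estimates the error. The documents support neither: the direction and size depend on who receives which treatment and on how well the measured covariates capture that choice, and every input to the illustrations is assumed. The matter should be settled before the sub-study 5 models are built; it does not affect the other sub-studies' prediction objectives.

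**What to change.** Choose one of two routes and state it under sub-study 5.

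1. **Keep the selection objective.** Estimate OS contrasts between named treatment classes, with time zero at second-line start. Adjust for confounders measured at that time by IPTW or a doubly robust estimator, restricted to patients with propensity overlap. List those confounders in the sub-study's data collection. Judge the rule by weighted OS under the recommended versus other treatment, report AUC as a secondary measure, and state residual unmeasured confounding as a limit.
2. **Narrow the objective.** Reword the primary objective and the two matching secondary objectives as predicting prognosis after progression given the treatment received. The stated metrics then address the question asked.

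The first route costs more analysis work, collection of any listed confounder not already recorded, and a smaller analysable set where overlap is poor. The second needs only rewording, at the price of a narrower claim.
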